5.2 Covariates

It is presumed that the heterogeneous composition of the migrant population by country of birth within the study sites, and the type of centre (urban/rural), might have an influence on the impact and performance of the ISMiHealth tool. It is hypothesised that a higher detection rate and screening performance for specific conditions will be associated with migrants coming from endemic areas and/or high prevalent areas, as well as regarding the type of centre.

5.3 Missing data

A limitation of the retrospective data extraction is the possibility of a sizable number of missing values. All available data of the variables will be described and the proportions of missing values will be reported. If the percentage of missing data is high (\geq 50%), listwise deletion -deleting observations with more than one missing value- or dropping variables -discarding variables with a big amount of missing data- will be carried out.

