2.3 Endpoints

Primary Endpoints

Endpoint 1: For the detection rate of all aggregated infections, the monthly detection rate based on positive serologies, chest radiographies, the International Classification of Diseases Ninth Revision (ICD-9 for Andalusia) or Tenth Revision (ICD-10 for Catalonia) of FGM and/or gynaecologist referrals will be considered within the migrant patients who visited their assigned centre during the intervention period. Also, positive tuberculin skin test (TST) and/or Interferon Gamma Release Assay (IGRA) and stool samples will be considered for the Andalusian site. Control and intervention PCCs will be compared before and after the implementation.

Secondary Endpoints

Endpoint 2: For the detection rate of each individual condition, the infections and FGM, the monthly detection rate based on positive serologies, chest radiographies, ICD-9/ICD-10 of FGM and/or gynaecologist referrals, TST/IGRA and stool samples (for Andalusia) will be considered within the migrant patients who visited their assigned centre during the intervention period. Control and intervention PCCs will be compared before and after the implementation.

Endpoint 3: The number of early diagnoses of HIV will be assessed using the CD4 cell count of migrant patients diagnosed with an HIV infection, and will be compared between the control

and intervention PCCs before and after the implementation. If possible, we will estimate the monthly detection rate of early HIV diagnoses and also compare it between the intervention and control PCCs.

Endpoint 4: The number of early diagnoses of HBV and HCV will be assessed using the levels of transaminases, platelets, bilirubin, and clotting parameters from blood analyses of migrant patients diagnosed with HBV or HCV, and will be compared between the control and intervention PCCs before and after the implementation. If possible, we will estimate the monthly detection rate of individuals diagnosed with HBV or HCV presenting high levels of transaminases, platelets, bilirubin, and clotting parameters and also compare it between the intervention and control PCCs.

Endpoint 5: The number of the screening tests performed of all aggregated infections (serological tests, chest radiographies, TST or IGRA tests and stool samples in the case of the Andalusian site) will be compared between the intervention and control PCCs before and after the implementation.

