5.1 Timing of Analyses

In the Catalan Institute of Health, data will be extracted retrospectively after the year of implementation from the EPR system (eCAP) by the Information Technology (IT) staff of the Sistema d'Informació per al Desenvolupament de la Investigació en Atenció Primària (SIDIAP). The study variables will be pseudo-anonymized, with technical and functional separation, by a SIDIAP data manager. SIDIAP will be responsible for the data processing in Catalonia. Regarding SIDIAP source data, the strict SIDIAP security standards will be followed.

In Andalusia, the data will be extracted retrospectively after the year of implementation by a specialized IT committee of the Andalusian Health Service Institution of the area involved in this project (Almería). The information will be extracted retrospectively and will include: 1) the check-list from the tool and 2) the demographic and clinical variables. Then, the IT committee will link this information with the laboratory data of the reference hospital (Hospital de Poniente in Almeria) and will pseudo-anonymize the data.

Thereafter, the biostatistician responsible for the data analysis will have access to the pseudo-anonymized data. The pseudo-anonymized data, which will be analysed after the year of intervention is completed, will include the variables detailed in Annex 1 for the targeted migrant population of the PCCs of Catalonia and Andalusia included in the study.

In any case, the data from the Catalonian centres will be analysed separately from data of the PCCs from Almeria where a process evaluation will be performed and only preliminary effectiveness data will be estimated.

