intervention level. Linear regressions will be performed for the monthly detection rates of the aggregated infections, and of each individual condition, comparing the intervention and control centres before and during the intervention period.

- Other secondary outcomes will be the proportion of screening tests performed for the aggregated infections and for each individual condition, and factors associated with having a higher screening performance. For this, associations with continuous variables will be evaluated using t-tests, or one-way analysis of variance (one-way ANOVA) for normally distributed quantitative variables, while for not normally distributed quantitative variables, Wilcoxon Rank-Sum and Kruskal-Wallis tests will be carried out. Pearson's chi-square test or Fisher's exact test will be performed to evaluate the associations between categorical variables. In addition, odds ratio (OR) will be estimated (Table 3). Mixed effects logistic regression models will be carried out to identify associations between the screening performance and socio-demographic and epidemiological characteristics, and adjusted odds ratio (aOR) will be estimated, using the region of the PCC as a random intercept (Table 3).
- **b.** The **prevalence** of each individual condition will be estimated and reported with its respective 95%CI. The prevalence for each infection was defined as the number of diagnoses identified by the screening tests performed among the people that were tested. Serology tests will be contemplated for HIV, HBV, HCV, *T.cruzi*, *S.stercoralis* and *Schistosoma spp.* infections; for active TB, chest radiographies will be examined; for FGM, the completed questionnaires and/or referrals to specialists will be considered.

See table 4 for details of the methodology employed for the outcomes.

Data analysis in Andalusia

A similar analysis approach will be carried out in Andalusia but the limited number of PCCs may prevent to estimate the health impact of the tool, therefore, we plan to estimate preliminary effectiveness data. In addition, the analysis for syphilis, latent TB and intestinal parasites will be executed. Nevertheless, because the pilot study will be conducted in six PCCs of one area (Almería), we won't be able to carry mixed-effects logistic regression models and instead, multiple logistic regressions will be performed.

7. Tables and Figures

Table 1. Description of the ISMiHealth sample.

| Variables | Summary statistics | | |

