| Migrants tested for active TB | N (%) |
| Migrants tested for latent TB [^] | N (%) |
| Migrants tested for a T.cruzi infection | N (%) |
| Migrants tested for a S. stercoralis infection | N (%) |
| Migrants tested for a Schistosoma spp. infection | N (%) |
| Migrants tested for intestinal parasites^ | N (%) |
| Migrants screened for FGM | N (%) |
| Migrants diagnosed with HIV | N (%) |
| CD4 cell count | Mean (SD) or Median (IQR) |
| HIV viral load | Mean (SD) or Median (IQR) |
| Migrants diagnosed with syphilis^ | N (%) |

| Migrants diagnosed with HBV | N (%) |
|--|---------------------------|
| Migrants diagnosed with HCV | N (%) |
| Migrants diagnosed with active TB | N (%) |
| Migrants diagnosed with latent TB [^] | N (%) |
| Migrants diagnosed with T.cruzi infection | N (%) |
| Migrants diagnosed with S.stercoralis infection | N (%) |
| Migrants diagnosed with Schistosoma spp. infection | N (%) |
| Migrants diagnosed with intestinal parasites^ | N (%) |
| Laboratory parameters | Mean (SD) or Median (IQR) |
| Migrants diagnosed with FGM | N (%) |
| Referrals to specialists | N (%) |
| Other diagnoses | N (%) |
| Comorbidities | N (%) |
| Drugs prescribed during the intervention | N (%) |
| Medication adherence (in days) | Mean (SD) or Median (IQR) |
| Hospitalised patients | N (%) |
| Diagnoses during hospitalisation | N (%) |
| Time hospitalised | Mean (SD) or Median (IQR) |
| Patients who needed Intensive Care Unit | N (%) |
| Drugs prescribed during hospitalisation | N (%) |
| Medication adherence of drugs prescribed during | Mean (SD) or Median (IQR) |
| hospitalisation (in days) | |
| Follow-up visits after hospitalisation | Mean (SD) or Median (IQR) |
| Diagnoses made during follow-up visits after hospitalisation | N (%) |
| Drugs prescribed during follow-up visits after hospitalisation | N (%) |
| Medication adherence of drugs prescribed in follow-up | Mean (SD) or Median (IQR) |
| visits after hospitalisation (in days) | |
| Cured patients | N (%) |
| Patients who died during the intervention period | N (%) |

HIV: human immunodeficiency virus, HBV: hepatitis B virus, HCV: hepatitis C virus, TB: tuberculosis, FGM: female genital mutilation, SD: standard deviation, IQR: interquartile range; N = frequency

Table 3. Associations of different factors with XX tests performed

| Variables | XX test performed n/N (%) | OR (95% CI) | p. value | aOR (95% CI) | p. value |

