|---------------------------------|---------------------------------|----------------|----------|-----------------|----------|
| Centre | | | | | |
| Type of centre (urban or rural) | | | | | |
| Index of socioeconomic | | | | | |
| deprivation (MEDEA index) | | | | | |
| Arm of the intervention | | | | | |
| Patient | | | | | |
| Sex | | | | | |
| Age | | | | | |
| Area of birth^ | | | | | |
| Assigned PCT | | | | | |

| Referrals to specialists | | | |
|-----------------------------------|--|---|--|
| Drugs prescribed during the | | | |
| intervention | | | |
| Other diagnoses | | | |
| Immunosuppression status | | | |
| Migrants with screening criteria | | | |
| for XX^ | | | |
| CD4 cell count, viral load and/or | | | |
| laboratory parameters* | | | |
| Hospitalisation | | | |
| Follow-up visits after | | | |
| hospitalisation | | | |
| Mortality | | _ | |

PCT: primary care team, XX: aggregated infections or any of the conditions, OR: odds ratio, aOR: adjusted odds ratio, CI: confidence interval; Region will be used as a random intercept for the logistic regressions; ^Only one of these variables will be added to the multiple logistic regression model due to highly correlation; *When applicable

Table 4. Description of the methodology employed for each outcome

| Outcome | | Methodology |
|--|---------------------------------|------------------------------------|
| Detection rate of all aggre | gated infections | Difference in differences analysis |
| | HIV cases | |
| | Syphilis cases^ | |
| | HBV cases | |
| Detection rate of each | HCV cases | Difference in differences |
| individual condition | active TB cases | analysis |
| | latent TB cases^ | |
| | T.cruzi infection cases | |
| | S.stercoralis infection cases | |
| | Schistosoma spp. infection | |
| | cases | |
| | Intestinal parasites cases^ | |
| | FGM cases | |
| Early diagnoses of | HIV | Bivariate analysis and, if |
| infections | HBV | possible, difference in |
| | HCV | differences analysis |
| Screening tests performed of all aggregated infections | | Bivariate analysis |
| | HIV | |
| | Syphilis^ | |
| | HBV | |
| Screening tests | HCV | |
| performed for each | active TB (chest radiographies) | Bivariate analysis |
| individual condition | latent TB^ (TST/IGRA) | |
| | T.cruzi infections | |
| | S.stercoralis infections | |
| | Schistosoma spp. infections | |

| | Intestinal parasites^ | |
|----------------------------|-----------------------------|--------------------------------|

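### The SAP 5.3 delete-or-drop rule does not protect endpoint-defining variables, and Table 3 lets post-test fields into the models for test performed

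*SAP*

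**What the plan says.** SAP 5.3 expects that retrospective extraction may leave many values missing. It commits to describing the available data and reporting the proportions missing. If missingness is 50% or more, the action is "listwise deletion -deleting observations with more than one missing value- or dropping variables -discarding variables with a big amount of missing data". The section does not say which action applies when, what the percentage is a percentage of, or what happens below 50%. It exempts no variable.

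The rule operates on a file that "will include the variables detailed in Annex 1 for the targeted migrant population of the PCCs" (SAP 5.1). Two secondary endpoints in SAP 2.3 rest on fields in that file:

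- Endpoint 3 (early HIV diagnosis) is assessed "using the CD4 cell count of migrant patients diagnosed with an HIV infection".
- Endpoint 4 (early HBV and HCV diagnosis) uses "levels of transaminases, platelets, bilirubin, and clotting parameters from blood analyses of migrant patients diagnosed with HBV or HCV".

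For Endpoints 7 and 8, SAP section 6 states: "Mixed effects logistic regression models will be carried out to identify associations between the screening performance and socio-demographic and epidemiological characteristics". The matching shell, Table 3, is headed "XX test performed n/N" and has crude and adjusted odds-ratio columns. Its rows include arm, referrals, drugs prescribed, hospitalisation, follow-up visits, mortality, and a row that begins "CD4 cell count, viral load and/or" and continues to laboratory parameters. That row's asterisk leads to a footnote ending "due to highly correlation; *When applicable".

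**The concern.** Two things go wrong, and they reinforce each other.

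First, a rule meant for sparse covariates is written so that it also covers the fields that define Endpoints 3 and 4. Discarding a sparse covariate costs some adjustment; discarding CD4 removes Endpoint 3. The data are extracted and analysed only after the intervention year, so the choice between deleting and dropping would be made with the data in hand.

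Second, the factors offered for test performed include fields that a patient can have only once tested or diagnosed. CD4 and viral load follow an HIV diagnosis. Annex 1 defines referral as due to a diagnosis during the intervention. Death cannot precede a test. A model for being tested that conditions on such fields, or drops patients without them, no longer compares arms in the population that was eligible for testing. Arm is one of the factors whose odds ratio is to be reported, so the effect of the tool on screening is directly exposed.

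**Working it through.** SAP 5.3 states no figure to reproduce beyond the 50% threshold. The documents give no recording rates, so every availability value below is an assumption.

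**1. Does the rule reach an endpoint variable when missingness is counted only among patients to whom it applies?**

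Share missing = 1 − share recorded. For CD4 among HIV-diagnosed patients:

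| Recorded (assumed) | Missing | 50% rule reached |
|---|---|---|
| 30% | 70% | yes |
| 50% | 50% | yes |
| 70% | 30% | no |
| 100% | 0% | no |

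The same arithmetic holds for each Endpoint 4 field among HBV- or HCV-diagnosed patients. Once the threshold is reached, 5.3 permits discarding the field, and no other section forbids it.

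**2. How much can deletion remove?**

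Annex 1 has 13 primary-care laboratory fields. Suppose each is 50% missing and an observation is a patient. If the fields are always missing together, 50% of patients have more than one missing value. If they are missing independently, the share is 1 − (0.5¹³ + 13 × 0.5¹³) = 1 − 14/8192 = 99.8%. Below the threshold 5.3 is silent: one covariate 49% missing removes 49% of patients from a regression without imputation.

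**3. What does selection do to the arm odds ratio?**

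Let a1 and a0 be the shares kept among tested and untested patients in an arm, and r = a1/a0. Selection multiplies the odds of being tested in that arm by r, so for the unadjusted estimate

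kept OR = true OR × r(intervention) / r(control).

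There is no bias if r is equal in the two arms, even when tested patients are kept far more often than untested ones. An illustration with a1 = 0.80 in both arms and a0 = 0.25 in control, so r(control) = 0.80/0.25 = 3.2:

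| a0, intervention (assumed) | r(intervention) | Factor on OR |
|---|---|---|
| 0.20 | 4.00 | 1.25 |
| 0.25 | 3.20 | 1.00 |
| 0.3125 | 2.56 | 0.80 |

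Direct check of the first row with 15% tested in both arms (true OR 1.00): tested kept is 0.15 × 0.80 = 0.12 in each arm; untested kept is 0.85 × 0.20 = 0.17 against 0.85 × 0.25 = 0.2125. The kept OR is (0.12/0.17)/(0.12/0.2125) = 1.25.

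The limiting case is CD4 as a covariate in the model for HIV testing. Almost everyone kept would be HIV-diagnosed, a0 would be near zero, and there would be few or no untested comparators.

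**The case against.** The strongest reply has four parts.

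- **CD4 is tied to diagnosed patients.** A reader might infer that the rule certainly discards CD4, because over the whole migrant file it would be 95% to 99.8% empty (assumed HIV share 5% down to 0.2%, CD4 complete in every case). The documents do not support that. Endpoint 3 confines CD4 to HIV-diagnosed patients, and Table 2 lists it directly under the count diagnosed with HIV. A blank in someone without HIV is not applicable, and literal whole-file deletion would remove nearly everyone without HIV. The same limit holds for Endpoint 4. This part stands.
- **If half the CD4 values are missing, Endpoint 3 is in trouble under any rule.** True, but a weak endpoint reported with its missingness by arm is better than one removed at the analyst's choice.
- **The models are described as socio-demographic and epidemiological.** Section 6 does say so. Protocol section 5 describes country of origin, age and sex as routinely collected, and the Table 3 laboratory row applies only when applicable. However, Table 3 gives the post-test rows the same adjusted column as arm, and no text says which rows are left out of the model.
- **Bias in the arm odds ratio is possible, not shown.** This stands. The protocol's screening procedures do not include transaminases, bilirubin, platelets or clotting tests, so a differential effect of the tool on their availability is conjecture. The retention shares above are invented, and the factors fall on both sides of 1.

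Reading observations as patients is also an interpretation.

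**Conclusion.** The concern holds as a defect in an operative rule and in the Table 3 covariate list, at the level of secondary endpoints. Endpoints 3 and 4 can be lost if their defining fields are recorded in half or fewer of the relevant diagnosed patients; whether that will happen cannot be told from the documents. The arm odds ratio in Endpoints 7 and 8 can be biased if post-test fields enter the models or govern deletion, and if retention differs jointly by test status and arm. Neither sign nor size can be claimed, and the factors of 0.80 to 1.25 only illustrate the algebra.

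A reader might infer that the primary outcome is compromised. It is built from monthly diagnosis counts, and Endpoints 5 and 6 from tests performed; these change only if deletion is applied to the records behind the counts, which 5.3 neither orders nor excludes. The unstated denominator and the silence below 50% are missing detail and would not carry the point alone. The commitment to report proportions missing makes the problem visible but does not resolve it. The change should be made before the data are analysed.

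**What to change.** Replace the rule in SAP 5.3 and trim Table 3:

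1. No patient is removed from a detection or screening numerator or denominator because of missing covariates or laboratory values.
2. Percent missing is calculated per variable among patients to whom it applies: HIV-diagnosed for CD4 and viral load, HBV- or HCV-diagnosed for the Endpoint 4 laboratory values. A value not measured in such a patient counts as missing. Endpoint-defining variables are never dropped, and the number missing is reported by arm and period.
3. Dropping at 50% or more applies only to baseline covariates, and any deletion is limited to the covariates in the given model.
4. Fields that arise only after testing or diagnosis are removed from the Table 3 models for test performed and shown descriptively.
5. One method for missing baseline covariates, at any percentage, is pre-specified with a sensitivity analysis. Multiple imputation including arm and centre, with complete cases as the sensitivity analysis, is one option among several.

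The cost is SAP wording, a few Table 3 rows that become descriptive only, and modest extra analysis, somewhat more if imputation is chosen for a large clustered extract. No new data are needed.

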5.4 Interim Analysis and Data Monitoring

No interim analysis will be conducted. However, the Sistema d'Informació dels Serveis d'Atenció Primària (SISAP) will supervise the technical monitoring of the tool in the implementation phase of the study. Simultaneously, aggregated data will be obtained via SIDIAP during the process of implementation of the tool in the Catalan Institute of Health with the sole objective of technical monitoring to identify alert errors and provide subsequent remediation.

6. Data analysis

Since the ISMiHealth tool is in different phases of implementation in each site, and the algorithms are based on different recommendations, there will be two independent data analyses: i) in Catalonia, the health impact of the tool will be evaluated in 35 PCCs; and ii) in Andalusia, the preliminary effectiveness data will be estimated in the six PCCs where the tool will be pilot tested.

The precision for the reporting of the results will be 95%, considering statistically significant p.values<0.05.

First, for the description of the sample and data obtained from the screening program in each study site, summary statistics will be presented as frequencies for categorical variables, as means with standard deviations (SD) for normally distributed continuous variables and medians with interquartile range (IQR) for non-normally distributed continuous variables (Table 1 and 2).

Data analysis in Catalonia

- a. Health impact of the tool. The effectiveness of the tool will be evaluated and compared between the intervention and control centres. Significant deviations between intervention and control centres before the implementation of the screening program will be suggestive of the main underlying assumption, presenting parallel trends prior to implementation.
 - The primary outcome of the study will be the detection rate of the aggregated infections, while the detection of the individual conditions will be considered as secondary outcomes of the study. To analyse the effect of the intervention on the outcomes, difference in differences approach will be performed using a generalized linear model. Intervention and control PCCs will be compared before and after implementation with respect to the monthly detection rate. Standard errors will be clustered at the

intervention level. Linear regressions will be performed for the monthly detection rates of the aggregated infections, and of each individual condition, comparing the intervention and control centres before and during the intervention period.

- Other secondary outcomes will be the proportion of screening tests performed for the aggregated infections and for each individual condition, and factors associated with having a higher screening performance. For this, associations with continuous variables will be evaluated using t-tests, or one-way analysis of variance (one-way ANOVA) for normally distributed quantitative variables, while for not normally distributed quantitative variables, Wilcoxon Rank-Sum and Kruskal-Wallis tests will be carried out. Pearson's chi-square test or Fisher's exact test will be performed to evaluate the associations between categorical variables. In addition, odds ratio (OR) will be estimated (Table 3). Mixed effects logistic regression models will be carried out to identify associations between the screening performance and socio-demographic and epidemiological characteristics, and adjusted odds ratio (aOR) will be estimated, using the region of the PCC as a random intercept (Table 3).
- **b.** The **prevalence** of each individual condition will be estimated and reported with its respective 95%CI. The prevalence for each infection was defined as the number of diagnoses identified by the screening tests performed among the people that were tested. Serology tests will be contemplated for HIV, HBV, HCV, *T.cruzi*, *S.stercoralis* and *Schistosoma spp.* infections; for active TB, chest radiographies will be examined; for FGM, the completed questionnaires and/or referrals to specialists will be considered.

See table 4 for details of the methodology employed for the outcomes.

Data analysis in Andalusia

A similar analysis approach will be carried out in Andalusia but the limited number of PCCs may prevent to estimate the health impact of the tool, therefore, we plan to estimate preliminary effectiveness data. In addition, the analysis for syphilis, latent TB and intestinal parasites will be executed. Nevertheless, because the pilot study will be conducted in six PCCs of one area (Almería), we won't be able to carry mixed-effects logistic regression models and instead, multiple logistic regressions will be performed.

7. Tables and Figures

Table 1. Description of the ISMiHealth sample.

| Variables | Summary statistics | | |
|--|---------------------------|--|--|
| PC professional | | | |
| Primary care team (PCT) | N (%) | | |
| Type of health professional | N (%) | | |
| Professional category | N (%) | | |
| Sex | N (%) | | |
| Age | Mean (SD) | | |
| Centre | | | |
| Region | N (%) | | |
| Type of centre (urban or rural) | N (%) | | |
| Index of socioeconomic deprivation (MEDEA index) | Mean (SD) or Median (IQR) | | |
| Number of professionals (general practitioners and nurses) | Mean (SD) or Median (IQR) | | |
| Migration density | Mean (SD) or Median (IQR) | | |

| Number of migrants assigned to the centres | Mean (SD) or Median (IQR) |
|---|---------------------------|
| Number of migrants who did not visit the centres during the | Mean (SD) or Median (IQR) |
| intervention | |
| Number of migrants with at least one visit during the | Mean (SD) or Median (IQR) |
| intervention period | |
| Arm of the intervention | N (%) |
| Patient | |
| Sex | N (%) |
| Age | Mean (SDI) |
| Area of birth | N (%) |
| Assigned PCT | N (%) |
| Assigned health professional | N (%) |
| Time registered in the healthcare system | Mean (SD) or Median (IQR) |
| Number of visits | Mean (SD) or Median (IQR) |
| Immunosuppression status | N (%) |
| Migrants with screening criteria for HIV | N (%) |
| Migrants with screening criteria for syphilis^ | N (%) |
| Migrants with screening criteria for HBV | N (%) |
| Migrants with screening criteria for HCV | N (%) |
| Migrants with screening criteria for active TB | N (%) |
| Migrants with screening criteria for latent TB [^] | N (%) |
| Migrants with screening criteria for a T.cruzi infection | N (%) |
| Migrants with screening criteria for a S. stercoralis infection | N (%) |
| Migrants with screening criteria for a Schistosoma spp. | N (%) |
| infection | |
| Migrants with screening criteria for intestinal parasites^ | N (%) |
| Migrants with screening criteria for FGM | N (%) |
| | 1 |

PC: primary care, PCT: primary care team, HIV: human immunodeficiency virus, HBV: hepatitis B virus, HCV: hepatitis C virus TB: tuberculosis, FGM: female genital mutilation, SD: standard deviation, IQR: interquartile range; N = frequency

Table 2. Data obtained throughout the ISMiHealth screening program.

| Variables | Summary statistics |
|--|---------------------------|
| Migrants tested for HIV | N (%) |
| Migrants tested for syphilis^ | N (%) |
| Migrants tested for HBV | N (%) |
| Migrants tested for HCV | N (%) |
| Migrants tested for active TB | N (%) |
| Migrants tested for latent TB [^] | N (%) |
| Migrants tested for a T.cruzi infection | N (%) |
| Migrants tested for a S. stercoralis infection | N (%) |
| Migrants tested for a Schistosoma spp. infection | N (%) |
| Migrants tested for intestinal parasites^ | N (%) |
| Migrants screened for FGM | N (%) |
| Migrants diagnosed with HIV | N (%) |
| CD4 cell count | Mean (SD) or Median (IQR) |
| HIV viral load | Mean (SD) or Median (IQR) |
| Migrants diagnosed with syphilis^ | N (%) |

| Migrants diagnosed with HBV | N (%) |
|--|---------------------------|
| Migrants diagnosed with HCV | N (%) |
| Migrants diagnosed with active TB | N (%) |
| Migrants diagnosed with latent TB [^] | N (%) |
| Migrants diagnosed with T.cruzi infection | N (%) |
| Migrants diagnosed with S.stercoralis infection | N (%) |
| Migrants diagnosed with Schistosoma spp. infection | N (%) |
| Migrants diagnosed with intestinal parasites^ | N (%) |
| Laboratory parameters | Mean (SD) or Median (IQR) |
| Migrants diagnosed with FGM | N (%) |
| Referrals to specialists | N (%) |
| Other diagnoses | N (%) |
| Comorbidities | N (%) |
| Drugs prescribed during the intervention | N (%) |
| Medication adherence (in days) | Mean (SD) or Median (IQR) |
| Hospitalised patients | N (%) |
| Diagnoses during hospitalisation | N (%) |
| Time hospitalised | Mean (SD) or Median (IQR) |
| Patients who needed Intensive Care Unit | N (%) |
| Drugs prescribed during hospitalisation | N (%) |
| Medication adherence of drugs prescribed during | Mean (SD) or Median (IQR) |
| hospitalisation (in days) | |
| Follow-up visits after hospitalisation | Mean (SD) or Median (IQR) |
| Diagnoses made during follow-up visits after hospitalisation | N (%) |
| Drugs prescribed during follow-up visits after hospitalisation | N (%) |
| Medication adherence of drugs prescribed in follow-up | Mean (SD) or Median (IQR) |
| visits after hospitalisation (in days) | |
| Cured patients | N (%) |
| Patients who died during the intervention period | N (%) |

HIV: human immunodeficiency virus, HBV: hepatitis B virus, HCV: hepatitis C virus, TB: tuberculosis, FGM: female genital mutilation, SD: standard deviation, IQR: interquartile range; N = frequency

Table 3. Associations of different factors with XX tests performed

| Variables | XX test performed n/N (%) | OR (95% CI) | p. value | aOR (95% CI) | p. value |
|---------------------------------|---------------------------------|----------------|----------|-----------------|----------|
| Centre | | | | | |
| Type of centre (urban or rural) | | | | | |
| Index of socioeconomic | | | | | |
| deprivation (MEDEA index) | | | | | |
| Arm of the intervention | | | | | |
| Patient | | | | | |
| Sex | | | | | |
| Age | | | | | |
| Area of birth^ | | | | | |
| Assigned PCT | | | | | |

| Referrals to specialists | | | |
|-----------------------------------|--|---|--|
| Drugs prescribed during the | | | |
| intervention | | | |
| Other diagnoses | | | |
| Immunosuppression status | | | |
| Migrants with screening criteria | | | |
| for XX^ | | | |
| CD4 cell count, viral load and/or | | | |
| laboratory parameters* | | | |
| Hospitalisation | | | |
| Follow-up visits after | | | |
| hospitalisation | | | |
| Mortality | | _ | |

PCT: primary care team, XX: aggregated infections or any of the conditions, OR: odds ratio, aOR: adjusted odds ratio, CI: confidence interval; Region will be used as a random intercept for the logistic regressions; ^Only one of these variables will be added to the multiple logistic regression model due to highly correlation; *When applicable

Table 4. Description of the methodology employed for each outcome

| Outcome | | Methodology |
|--|---------------------------------|------------------------------------|
| Detection rate of all aggre | gated infections | Difference in differences analysis |
| | HIV cases | |
| | Syphilis cases^ | |
| | HBV cases | |
| Detection rate of each | HCV cases | Difference in differences |
| individual condition | active TB cases | analysis |
| | latent TB cases^ | |
| | T.cruzi infection cases | |
| | S.stercoralis infection cases | |
| | Schistosoma spp. infection | |
| | cases | |
| | Intestinal parasites cases^ | |
| | FGM cases | |
| Early diagnoses of | HIV | Bivariate analysis and, if |
| infections | HBV | possible, difference in |
| | HCV | differences analysis |
| Screening tests performed of all aggregated infections | | Bivariate analysis |
| | HIV | |
| | Syphilis^ | |
| | HBV | |
| Screening tests | HCV | |
| performed for each | active TB (chest radiographies) | Bivariate analysis |
| individual condition | latent TB^ (TST/IGRA) | |
| | T.cruzi infections | |
| | S.stercoralis infections | |
| | Schistosoma spp. infections | |

| | Intestinal parasites^ | |
|----------------------------|-----------------------------|--------------------------------|
| | FGM (completed | |
| | questionnaires) | |
| Associations with the scre | ening performance for all | Bivariate and multivariate |
| aggregated infections | | analysis |
| | HIV | |
| | Syphilis^ | |
| Associations with the | HBV | Bivariate and multivariate |
| screening performance | HCV | analysis |
| for each individual | active TB | |
| condition | latent TB^ | |
| | T.cruzi infections | |
| | S.stercoralis infections | |
| | Schistosoma spp. infections | |
| | Intestinal parasites^ | |
| | FGM | |
| Patients under follow-up a | after diagnosis | Bivariate analysis |
| Patients under treatment | after diagnosis | Bivariate analysis |
| Cured patients | | Bivariate analysis |
| | HIV | |
| | Syphilis^ | |
| | HBV | Numerator: number of |
| Prevalence of each | HCV | detected cases for each |
| condition | active TB | specific condition. |
| | latent TB^ | Denominator : number of |
| | T.cruzi infections | tested patients for each |
| | S.stercoralis infections | specific condition. |
| | Schistosoma spp. infections | |
| | Intestinal parasites^ | |
| | FGM | |

HIV: human immunodeficiency virus, HBV: hepatitis B virus, HCV: hepatitis C virus, TB: tuberculosis, FGM: female genital mutilation, TST: tuberculin skin test, IGRA: Interferon Gamma Release Assay; ^Only in the Andalusian site; The detection rate of all aggregated infections and the individual conditions will be calculated using the numbers of diagnoses per month over at least five years until the end of the intervention.

Figure 1. Flow chart of the migrant population

Figure 2. Monthly detection rates of the aggregated infections

Figure 3-9. Monthly detections of each individual condition (infections and FGM)

8. Reporting Conventions

Dates will be reported using the format MM/DD/YYYY. P-values will be reported to 3 decimal places. P-values less than 0.001 will be reported as '<0.001'. Statistics such as means, standard deviations, median values and percentages, will be calculated using the same decimal digits as the raw data. Rounding off will be performed on the final calculation value and reported according to publication requirements.

9. Technical Details

The data of the ISMiHealth study will be analysed with Stata Statistical Software: Release 16. At the time of the writing, the operating system of the computer that will be used for the analysis is Windows.

10. Summary of Changes to the Protocol

